13.7 Interim Analysis

No Interim analyses are planned.

13.8 Sample Size Calculation

The one-arm study will assess the efficacy of perampanel for the treatment of primary brain tumor patients with partial onset seizures. The basis for this assessment is the percentage of patients with a $\geq 50\%$ seizure reduction during the treatment period compared with the seizure frequency before initiation of perampanel (i.e. 50% responder rate).

Several recently conducted randomized studies of patients with partial-onset seizures have reported a 50% responder rate of approximately 20% within the standard treatment arm.²⁻⁴ Steinhoff (2009) also reports a 50% responder rate of approximately 35% within a general population of patients with partial-onset seizures treated with perampanel.²

This study has been designed with 90% power to detect an increase in the 50% responder rate during the treatment period from a benchmark of 20% to 35%. Assuming a type I error rate of 0.1, 61 patients will be required. Based on prior studies the early discontinuation rate was 16%, therefore 71 patients will be enrolled to compensate for patients discontinuing prior to the completion of the treatment period.

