3.5 Data Analysis and Statistical Considerations

The one-arm study will assess the efficacy of perampanel for the treatment of primary brain tumor patients with partial onset seizures. The basis for this assessment is the percentage of patients with a $\geq 50\%$ seizure reduction during the treatment period compared with seizure frequency before initiation of perampanel (i.e. 50% responder rate).

Several recent conducted randomized studies of patients with partial-onset seizures have reported a 50% responder rate of approximately 20% within the standard treatment arm.²⁻⁴ Steinhoff (2009) also reports a 50% responder rate of approximately 35% within a general population of patients with partial-onset seizures treated with perampanel.⁵

This study has been designed with 90% power to detect an increase in the 50% responder rate during the treatment period from a benchmark of 20% to 35%. Assuming a type I error rate of 0.1, 61 patients will be required. Based on prior studies the early discontinuation rate was 16%, therefore 71 patients will be enrolled to compensate for patients discontinuing prior to the completion of the treatment period.

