7 INVESTIGATIONAL PLAN

7.1 Study Design

This is a Phase 4 single-arm study assessing the efficacy of perampanel as an adjunct anti-epileptic drug (AED) in patients with primary glioma presenting refractory partial onset seizure activity (defined as 3 or more seizures in a 28-day period). All primary glioma patients that have refractory partial onset seizures can be considered for this clinical trial if they meet the eligibility criteria. This will include patients that are receiving active chemotherapy, which could include, but is not limited to, the following agents: temozolamide, bevacizumab, irinotecan, etoposide, lomustine, carboplatin. All concomitant medications will be recorded during the study. The study will enroll approximately 71 patients at the PRTBTC at Duke.

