7.4 Definition of Evaluable Subjects, On Study, and End of Study

All patients who complete the treatment period will be included in the primary endpoint analysis. All patients who received protocol treatment, regardless of duration, will be included in the safety analysis.

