10.7.3 Replacement of Early Withdrawal(s)

Not applicable.

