13.1 Analysis Sets

As indicated in section 7.4, subject to the availability of data, all patients who receive perampanel treatment will be included in safety analyses. All patients who complete the treatment period of the study will be included in efficacy analyses.

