13.4.2 Statistical Hypothesis, Model, and Method of Analysis

As described in Section 3.5 and 13.8, this study has been designed to detect an increase in the 50% responder rate from a benchmark of 20% to 35%. A one-sample binomial test will test this hypothesis at the 0.1 level of significance.

As a related secondary analysis, seizure frequency will be estimated separately for each patient within the titration, treatment, tapering, and follow-up phases of treatment, and the percent reduction in seizure frequency relative to baseline computed. The distribution across patients within each treatment phase in the percent reduction will be described. Depending upon the distribution of these data, means and standard deviations may be used to describe the distribution of percent reduction or quartiles.

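### Enrolling 71 does not quite cover the stated 16% discontinuation: it gives about 60 completers, not 61, and about 89% power, not 90%

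*Combined protocol and SAP*

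**What the plan says.** Section 13.8, repeated in 3.5, sets a null responder rate of 20%, a target of 35%, a type I error rate of 0.1 and power of 90%, and arrives at 61 patients. It then allows for dropout: "Based on prior studies the early discontinuation rate was 16%, therefore 71 patients will be enrolled". Section 3.5 gives the purpose: "therefore 71 patients will be enrolled to compensate for patients discontinuing prior to the completion of the treatment period". Section 7.1 carries the number forward: "The study will enroll approximately 71 patients at the PRTBTC at Duke".

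Three other sections decide how many of the 71 count towards the primary test:

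- Section 7.4: "All patients who complete the treatment period will be included in the primary endpoint analysis".
- Section 13.1: "All patients who complete the treatment period of the study will be included in efficacy analyses".
- Section 10.7.3, on replacing patients who withdraw early, is marked not applicable.

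Section 13.4.2 names the test: "A one-sample binomial test will test this hypothesis at the 0.1 level of significance". It does not say whether the test is exact or one-sided, but the stated aim is to detect an increase.

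**The concern.** Section 13.8 presents 71 as following from 61 and 16%, and it does not follow. If 16% of those enrolled are lost, the number left is the enrolment times 0.84, so the enrolment needed is 61 divided by 0.84. The figure 71 is what one gets by adding 16% of 61 to 61 (61 × 1.16 = 70.8). The plan shows no formula, so that route is an inference, but the shortfall is the same whatever the route.

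The 16% falls directly on the primary analysis, because patients who stop before the end of the treatment period leave the efficacy set and no replacement is planned. What is at stake is modest: the evaluable number and power that the plan leads a reader to expect are slightly better than its own inputs deliver.

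**Working it through.** **Inputs.** Null rate 0.20, target rate 0.35, type I error 0.1, power 0.90, 61 required, 16% discontinuation, 71 enrolled (3.5 and 13.8). One-sample binomial test (13.4.2). Completers-only efficacy set (7.4, 13.1). No replacement planned (10.7.3).

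**Step 1: reproduce the 61.** For each n, take the smallest count c with P(X ≥ c | n, 0.20) ≤ 0.10. Power is then P(X ≥ c | n, 0.35).

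| n | c | attained alpha | power |
|---|---|---|---|
| 57 | 16 | 0.0908 | 0.8934 |
| 58 | 17 | 0.0585 | 0.8526 |
| 59 | 17 | 0.0675 | 0.8723 |
| 60 | 17 | 0.0772 | 0.8899 |
| 61 | 17 | 0.0879 | 0.9055 |
| 62 | 17 | 0.0995 | 0.9192 |
| 63 | 18 | 0.0657 | 0.8867 |

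The first n with power of at least 0.90 is 61, so the plan's figure is reproduced by a one-sided exact test. The usual one-sided approximations do not give it: the normal formula gives 57, or 63 with continuity correction, and the arcsine formula gives 58. The two-sided normal formula gives 72. One cruder formula also rounds to 61: two-sided normal with the null variance throughout, (1.645 + 1.282)² × 0.16 / 0.15² = 60.9. It does not fit a plan to detect an increase. It would not rescue the power either, since an exact test with 0.05 in the upper tail has power of only 0.850 at n = 61.

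**Step 2: the inflation.**

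- Expected completers from 71: 71 × (1 − 0.16) = 59.6.
- Enrolment for an expected 61: 61 / (1 − 0.16) = 72.6, so 73 (73 × 0.84 = 61.3).
- Loss that 71 can absorb: (71 − 61)/71 = 10/71 = 14.1%.
- Probable source of 71: 61 × 1.16 = 70.8, rounded up.

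**Step 3: power with 71 enrolled.** At 60 completers exact power is 0.890, and at 59 it is 0.872. The number of completers varies by chance, so power can also be averaged over a binomial count with completion probability 0.84:

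| enrolled | expected completers | P(at least 61 completers) | average exact power |
|---|---|---|---|
| 71 | 59.6 | 0.40 | 0.886 |
| 73 | 61.3 | 0.62 | 0.895 |
| 75 | 63.0 | 0.79 | 0.902 |

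At 74 the average is 0.8985, so 75 is the first enrolment whose average power reaches 90%.

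**The case against.** The arithmetic is not in dispute. The case against acting on it is that the point is too small and partly an artefact.

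- **Discreteness.** Exact power is saw-toothed: 63 completers (0.887) do no better than 60 (0.890). This stands, and it means the one-point drop from 61 to 60 should not be read as a smooth trend.
- **Mixed yardsticks.** Setting 0.905 at a fixed 61 beside an average of 0.886 for 71 enrolled overstates what the slip costs. Like for like, the averages are 0.886 for 71 and 0.895 for 73, a difference of about 0.8 points. The rest comes from random completer counts, which dividing by 0.84 would not remove. This stands too.
- **Choice of test.** The plan does not say exact or one-sided. Under a one-sided normal approximation, power at n = 60 is about 0.913 and never falls below 90%. But that formula would have given 57, not 61, so it is unlikely to be the design calculation. The shortfall in completers does not depend on the test.
- **Uncertain input.** The 16% is a planning value, and the standard deviation of the observed loss among 71 patients is √(0.16 × 0.84/71) = 4.4 percentage points. The actual loss could easily be 14% or less. That is true, but the plan chose 16% and says that 71 compensates for it.
- **What is claimed.** The plan ties 90% power to 61 patients, not to whatever number remains after dropout, and 7.1 says only approximately 71. That is a fair reading, but a reader told that 71 compensates for the loss will take 61 completers and 90% power as the expectation.

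These points limit the importance of the finding. They do not make 71 follow from 61 and 16%.

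**Conclusion.** The point holds, and it is minor. On the plan's own inputs, 71 enrolled gives 59.6 expected completers against 61 required, a gap of 1.4 completers or two enrolled patients (71 versus 73). Power is about 89%: 0.890 at 60 completers, or 0.886 on average. The study is not materially underpowered, and attained type I error at n = 60 is 0.077, within the 0.1 limit.

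The completer shortfall rests only on the 16% and the completers-only analysis without replacement. The power figures also assume a one-sided exact binomial test, inferred from the stated direction and from the match at 61. The averaged figures further assume that patients drop out independently, each with probability 0.16.

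**What to change.** In 3.5 and 13.8, replace the claim that 71 compensates for the loss with a statement that follows from the inputs: with 71 enrolled and 16% discontinuation, about 60 patients are expected to be evaluable, giving about 89% power with a one-sided exact binomial test at alpha 0.1. Note there that 73 enrolled would give an expected 61 completers, with average power of about 89.5%, so that 73 is not read as restoring a full 90%.

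In 13.4.2, as a clarification only, add that the test is one-sided and exact, so that the 61 can be reproduced.

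The cost is wording. Enrolment, test and analysis set are unchanged, and the stated power becomes about one point less favourable.

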14 ADMINISTRATIVE AND ETHICAL CONSIDERATIONS

14.1 Regulatory and Ethical Compliance

This protocol was designed and will be conducted and reported in accordance with the International Conference on Harmonization (ICH) Harmonized Tripartite Guidelines for Good Clinical Practice, the Declaration of Helsinki, and applicable federal, state, and local regulations.

14.2 DUHS Institutional Review Board and DCI Cancer Protocol Committee

The protocol, informed consent form, advertising material, and additional protocol-related documents must be submitted to the DUHS Institutional Review Board (IRB) and DCI Cancer Protocol Committee (CPC) for review. The study may be initiated only after the Principal Investigator has received written and dated approval from the CPC and IRB.

The Principal Investigator must submit and obtain approval from the IRB for all subsequent protocol amendments and changes to the informed consent form. The CPC should be informed about any protocol amendments that potentially affect research design or data analysis (i.e. amendments affecting subject population, inclusion/exclusion criteria, agent administration, statistical analysis, etc.).

The Principal Investigator must obtain protocol re-approval from the IRB within 1 year of the most recent IRB approval. The Principal Investigator must also obtain protocol re-approval from the CPC within 1 year of the most recent IRB approval, for as long as the protocol remains open to subject enrollment.

14.3 Informed Consent

The informed consent form must be written in a manner that is understandable to the subject population. Prior to its use, the informed consent form must be approved by the IRB.

The Principal Investigator or authorized key personnel will discuss with the potential subject the purpose of the research, methods, potential risks and benefits, subject concerns, and other study-related matters. This discussion will occur in a location that ensures subject privacy and in a manner that minimizes the possibility of coercion. Appropriate accommodations will be made available for potential subjects who cannot read or understand English or are visually impaired. Potential subjects will have the opportunity to contact the Principal investigator or authorized key personnel with questions, and will be given as much time as needed to make an informed decision about participation in the study.

Before conducting any study-specific procedures, the Principal Investigator must obtain written informed consent from the subject or a legally acceptable representative. The original informed consent form will be stored with the subject's study records, and a copy of the informed consent form will be provided to the subject. The Principal Investigator is responsible for asking the subject whether the subject wishes to notify his/her primary care physician about participation in the study. If the subject agrees to such notification, the Principal Investigator will inform the subject's primary care physician about the subject's participation in the clinical study.

14.4 Privacy, Confidentiality, and Data Storage

The Principal Investigator will ensure that subject privacy and confidentiality of the subject's data will be maintained. Research Data Security Plans (RDSPs) will be approved by the appropriate institutional Site Based Research group.

To protect privacy, every reasonable effort will be made to prevent undue access to subjects during the course of the study. Prospective participants will be consented in an exam room where it is just the research staff, the patient and his family, if desired. For all future visits, interactions with research staff (study doctor and study coordinators) regarding research activities will take place in a private exam room. All research related interactions with the participant will be conducted by qualified research staff who are directly involved in the conduct of the research study.

To protect confidentiality, subject files in paper format will be stored in secure cabinets under lock and key accessible only by the research staff. Subjects will be identified only by a unique study number and subject initials. Electronic records of subject data will be maintained using Excel, which is housed in an encrypted and password-protected file on a secure network drive. Access to electronic databases (without edit rights) will be limited to the PI, the study coordinator, and the statistical team. The security and viability of the IT infrastructure will be managed by the DCI and/or Duke Medicine.

Upon completion of the study, research records will be archived and handled per DUHS HRPP policy. Subject names or identifiers will not be used in reports, presentations at scientific meetings, or publications in scientific journals.

14.5 Data and Safety Monitoring

Data and Safety Monitoring will be performed in accordance with the DCI Data and Safety Monitoring Plan. For a more detailed description of the DSMP for this protocol, refer to Section 11 (Sections 11.3 and 11.4 in particular) and Section 12.

14.6 Protocol Amendments

All protocol amendments must be initiated by the Principal Investigator and approved by the IRB prior to implementation. IRB approval is not required for protocol changes that occur to protect the safety of a subject from an immediate hazard. However, the Principal Investigator must inform the IRB and all other applicable regulatory agencies of such action immediately.

14.7 Records Retention

The Principal Investigator will maintain study-related records for the longer of a period of:

- at least two years after the date on which a New Drug Application is approved by the FDA (if an IND is involved)
- at least two years after formal withdrawal of the IND associated with this protocol (if an IND is involved)
- at least six years after study completion (Duke policy)

14.8 Conflict of Interest

The Principal Investigator and Sub-Investigators must comply with applicable federal, state, and local regulations regarding reporting and disclosure of conflict of interest. Conflicts of interest may arise from

situations in which financial or other personal considerations have the potential to compromise or bias professional judgment and objectivity. Conflicts of interest include but are not limited to royalty or consulting fees, speaking honoraria, advisory board appointments, publicly-traded or privately-held equities, stock options, intellectual property, and gifts.

The Duke University School of Medicine's Research Integrity Office (RIO) reviews and manages research-related conflicts of interest. The Principal Investigator and Sub-Investigators must report conflicts of interest annually and within 10 days of a change in status, and when applicable, must have a documented management plan that is developed in conjunction with the Duke RIO and approved by the IRB/IEC.

14.9 Registration Procedure

Describe how new subject registration will occur.

16 APPENDICES

16.1 Appendix A: Cytochrome P450 Drug Interaction Table

Please see the following website for known cytochrome P450 inducers. The website is updated frequently as new information becomes available (Flockhart, 2007)²²:

<http://medicine.iupui.edu/clinpharm/ddis/main-table/>

16.2 Appendix B: Medication and Seizure Log

See attached.
